6.4 Sample Size and Power

Sample size estimation (Aim 1, SubAim 1a,1b). Similar to OPLS-DA, OPLS-R is a multivariate method for prediction. Different from hypothesis testing methods such as t-test or ANOVA, where sample size is determined by the power of rejecting null hypotheses when the alternative hypothesis is true, the sample size of OPLS-R is determined by its accuracy of prediction. In this study, we propose to recruit three groups of subjects (healthy men, pre- and postmenopausal women) with $n=60$ /group (estimated that $n=50$ /group will complete study). We plan to analyze all three groups together ($n=50*3=150$ subjects) to identify a formula for composite score that can predict choline pool size for all three groups. In case the universal score does not perform well, we will analyze each group ($n=50$ subjects) separately. Using our previous data with $n=44$ subjects, we successfully identified a panel of metabolites that can be used to predict whether a sample is taken at baseline or after choline deficient diet. As shown by the ROC plot, the area under curve was 98.77%, which indicates very high sensitivity and specificity (Figure 2). Our previous study indicates that there is a strong association between the panel of biomarkers and choline status even when the model was developed with a relatively small number of samples.

Sample size estimation (SubAim 1c). This analysis will first be applied to the *PEMT* SNPs (rs12325817-C; rs4646343-A and rs3760188-A) that are known to interact with the effect of dietary choline in women but not in men (24). This analysis serves to confirm the consistency between the performance of the choline status score and existing knowledge. Assuming the effect size of the diet \times genotype interaction is 0.6 (moderate effect), we

will have 89.61% of power to detect it at $P<0.05$ cutoff. The same analysis will then be performed for all other SNPs (>2 million) measured in this study. We will be under-powered for the global analysis after multiple testing adjustment for 2 million tests, so this analysis will be an exploratory analysis. To increase statistical power, we will use SNP based pathway enrichment analysis method (102). This analysis was developed for GWA studies, and addresses the lack of power issue in GWA studies. It will identify SNPs with jointly significant genetic effect, i.e. sharing the same biological pathways, even when the individual P value for each SNP may not be significant. The pathways identified from this analysis may provide insight into the regulation of choline metabolism.

7 STUDY INTERVENTION (drug, device or other intervention details)

Diets: The experimental diets, delivering 100%, 50% and 25% of the recommended intake of Cho (in all forms) (550 mg Cho/70 kg body weight/d), are identical except for the bread that we offer (Cho in the bread will be varied to deliver the desired Cho above that delivered by the base Cho diet as described previously (1)). The base Cho diet is composed of 0.8 g high biologic value protein/kg [current Recommended Dietary Allowance (RDA)], with 30% kcal coming from fat and the remaining kcal from carbohydrate; diets are prepared in-house to protocol specifications and are similar to those described in detail in a publication in JADA (1). These diets were designed to bracket the range of dietary intake observed in several large published human population studies (18-23, 75). We have experience using these limited Choline level diets for more than 60 days per subject in our previously published studies (10, 24, 25, 51, 55).

Total food intake will be adjusted to be isocaloric (using snacks that contain minimal choline in any form) and to provide adequate intakes of macro- and micronutrients. All diets meet or exceed the Estimated Average Requirement for methionine plus cysteine, and the RDI for vitamins B₁₂, B₆, and folate. A multivitamin supplement (Kirkland Signature Daily Multi Vitamins and Minerals; Costco, Seattle, WA) provides vitamins and minerals at or above the RDI or Adequate Intake. Subjects will also be given a dietary supplement containing the RDI of magnesium and 1.5 times the Adequate Intake of calcium (Calcium Magnesium Complex; Vitamin Shoppe, North Bergen, NJ). We will use a 3-day diet menu of equivalent diets to allow for meal diversity. On the day 12 of a diet period, subjects will consume 250mg Cho in the form of Cho chloride-(trimethyl-d9; 98%; Cambridge Isotope Laboratories, Tewksbury, MA, USA) replacing non-labeled Cho mole for mole in the bread. We will confirm total Cho content of diets by LC-MS/MS analysis of samples of duplicate food portions as previously described (1). Cho content and stability during storage of Cho in the bread will be separately determined.

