Test Article(s) (If Applicable)	The experimental diets, delivering 100%, 50% (to be determined by a pilot study) and 25% of the recommended intake of Cho (in all forms) (550 mg Cho/70 kg body weight/d), are identical except for the bread that we offer (Cho in the bread will be varied to deliver the desired Cho above that delivered by the base 25% Cho diet as described previously (1)). On day 12 of a diet period, subjects will consume 250mg Cho in the form of Cho chloride (trimethyl-d9). We will confirm total Cho content of diets by LC-MS/MS analysis of samples of duplicate food portions as previously described (1).

Study Design	Healthy volunteers (n=50 males, 50 premenopausal females and 50 postmenopausal females; 30 additional subjects for dropout replacement), will be randomly assigned to an order of 2 week intervals of diets where they consume meals that we provide containing 100% of the recommended intake of Cho (550 mg Cho/day), 50% of the recommended intake of Cho (275 mg Cho), and 25% of the recommended intake of Cho (137.5 mg Cho) for 2 weeks each. Each dietary interval is followed by a minimum 2 week washout period. On day 12 of each diet period, subjects will consume a bolus of 250mg of Cho in the form of Cho chloride-(trimethyl-d9). Before this bolus, a plasma sample will be collected to measure baseline enrichment of Cho isotopes. At the end of each diet period, plasma and urine samples will be collected for biomarker assays and isotopic dilution estimation of Cho pool size, and we will perform transient elastography (Fibroscan) of liver to assess liver fat. (see Fig. 1, appendix).

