Visit 3: On day 9 of the study subjects will pick up food for days 9-11. Subjects will be instructed to fast for day 12 serum sample.

Visit 4: On day 12 subjects will return to the NRI to pick up meals to be consumed on days 12-14. They will provide a fasted serum sample via venipuncture for baseline metabolomics and -d9 content of Cho metabolites and 0 hour and 6 hours (30 minute, 1 hour and 2 hour samples may also be collected). A bolus dose of Cho d9 will be given in a beverage immediately following the 0 hour blood draw. Subjects will also complete a simple muscle test (Biomedex) consisting of bicep curls. Subjects will be instructed to fast for day 13 serum sample. Participants will collect urine for 24 hours after bolus dose.

Visit 5: On day 13 subjects will provide fasted blood sample again and return 24 hour urine collection. They will pick up kit for subsequent 24 hour urine collection. Subjects will be instructed to fast for day 14 serum sample.

Visit 6: Subjects will provide fasted blood sample again and return 24 hour urine collection. They will pick up kit for subsequent 24 hour urine collection. Subjects will be instructed to fast for day 15 serum sample. UNC NRI will transport participants to Wake Translational Imaging Program in Winston Salem to complete MRS/MRI scans.

Visit 7: Subjects will arrive the morning of Day 15 for serum sample via venipuncture for metabolomics and Cho-d9 measurements. Subjects will return their 24 hour urine sample. A fibroscan test will be performed and, if female, a urine pregnancy test will be done. A heart rhythm strip and body composition measure will be obtained. This will complete the first arm of the study and will be followed by a two week washout period.

Visits 8-14: for the second arm of the study are the same as visits above, with the exception of the saliva for DNA.

Visits 15-21: for the third arm of the study are the same as visits above, with the exception of the saliva for DNA.

This concludes study participation.

4.3 Follow-up procedures (by visits):

If the clinical laboratory data remains within normal values, subjects will continue on to the next diet period. If any of the laboratory data is not within normal values at the end of any study period, subjects will be monitored as directed by abnormal lab values protocol (See Appendix Figure 6).

4.4 Unscheduled Visits:

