On the last 5 days of a diet period, subjects will consume 22% of their total dietary Cho in the form of Cho chloride-(trimethyl-d9; 98%; Cambridge Isotope Laboratories, Tewksbury, MA, USA). This proportion was shown by others to result in adequate enrichment of isotopic Cho in adults (89). This Cho will be diluted in the plasma pool of Cho and then in the liver and total body tissue pool of Cho, and metabolites will be formed (**Figure 5, appendix**). We will collect a plasma sample before (baseline) and after (post dosing) each 5-day feeding of deuterated Cho.

Cho is stored in the body primarily as Cho, phosphoCho, glycerophosphoCho, PtdCho and sphingomyelin. Acetylcholine and CDP-Cho constitute a very small portion of the Cho pool and will not be measured. In plasma, phosphoCho is hydrolyzed to Cho by alkaline phosphatase; thus, measuring enrichment of Cho includes a measure of phosphoCho. New Cho enters the pool from the diet and from *de novo* synthesis catalyzed by PEMT. The sum of the metabolite enrichments of Cho-d9, glycerophosphoCho-d9, sphingomyelin-d9 and PtdCho-d9 will be calculated relative to the sum of Cho compounds with no d9. The presence of Cho d3 compounds will be a measure of recycling of a methyl group into Cho via the PEMT pathway, and will be considered to be part of the unenriched Cho pool. Betaine d3 will not be considered part of the Cho pool, but its formation will allow us to adjust our assumptions as to how much of administered label is lost from the Cho pool compartment. We expect that betaine formation will be significant.

Isotope enrichments in each of the Cho-containing compounds will be measured using LC-MS/MSAs described above (89). We will calculate enrichment for each Cho-containing molecule as well as for the combination of the Cho molecules (total); we expect that total Cho enrichment will be what is used in our analyses, but examination of the enrichment of the individual Cho-containing species may allow us to refine our mathematical

compartment models for Cho distribution at 5 days.

Estimated total body Cho pool size is calculated using the following mass balance equations:

$$1. \quad (F_a \times a) + (F_b \times b) = (F_c \times c)$$

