Where F_a is the isotope abundance of deuterium in the isotopic dose; a is the amount of the absorbed isotopic dose (absorption assumed to be 100%); F_b is the isotope abundance of deuterium in the endogenous Cho pool (measured at baseline before 5-day deuterium treatment); b is the amount of the endogenous Cho pool at baseline; F_c is the isotope abundance of deuterium in the total Cho pool ($F = {}^2\text{H}/[{}^1\text{H} + {}^2\text{H}]$) after 5-day dosing; c is the amount of the total Cho pool after dosing.

F_a , F_b and F_c are measured by isotope ratio mass spectrometry.

a is calculated from administered dose

$$2. \quad c = a + b$$

$$3. \quad b = \text{body pool at baseline (unknown)} = a \frac{(F_a - F_c)}{F_c - F_b}$$

Though we will call the estimate derived from the above a measure of total body pool size, it is really just an estimate of the size of the pool that dietary Cho equilibrates with by 5 days (likely smaller than the total body pool). We must make a number of assumptions, discussed below, to arrive at such an estimate. Each assumption certainly affects our estimations of pool size, and as we collect data we will have to model outcomes if we alter these assumptions.

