6.3 Statistical Methods

Statistical methods (Aim 1, SubAim 1a,1b). Unsupervised principal component analysis will first be used to examine the clustering of samples from the diet periods, and to ensure that the QC pool replicates center in the samples from which they were derived. This will enable the evaluation of the stability of the platform across the plate and between days for the signals which have not yet been assigned, to remove any signals that are too random and prevent the desired clustering, and to identify subjects who outlie from their perspective diet periods. Supervised Orthogonal Partial Least Squares Regression (OPLS-R) will then be used to identify a panel of biomarkers, assign weight to each biomarker, and calculate a composite score to predict choline pool size. When we applied Orthogonal Partial Least Squares Effect Projections (OPLS-EP) and Orthogonal Partial Least Squares Discriminant Analysis (OPLS-DA) to our previous data, we identified a panel of biomarkers and calculated a composite score that successfully predicted choline status (baseline or depletion) for both men and women (**Figure 1**). In this proposed study, we will use OPLS-R instead of OPLS-DA, because choline pool size is a continuous variable, while choline status in our previous study was a categorical variable. We will analyze all of the samples using OPLS-R to identify a panel of biomarkers that predicts choline pool size universally for all three diet periods (healthy men, pre- and postmenopausal women). We will also consider performing the analysis for each diet period separately in case the universal panel does not provide high accuracy in prediction. For the purpose of validation, we will not split samples into training and testing sets, as it reduces the number of samples used for model building. Instead, prediction error will be estimated using the Bootstrap method, which was found by recent studies as providing “nearly unbiased estimates of future model performance without holding back data when making the final estimates of model parameters” (101). Variable Importance to Projection (VIP)

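### The Aim 1 score is trained on absolute choline pool size over men and women with no body-size term, so an unknown and possibly large share of the outcome may reflect body size rather than depletion

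*Combined protocol and SAP*

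**What the plan says.** - **Outcome.** Section 5.1 (isotope dilution): "Estimated total body Cho pool size is calculated using the following mass balance equations". There "b is the amount of the endogenous Cho pool at baseline", given by b = a(Fa − Fc)/(Fc − Fb), and "a is calculated from administered dose". No unit is stated for b; it takes the unit of the dose.
- **Model.** Section 6.3: "We will analyze all of the samples using OPLS-R to identify a panel of biomarkers that predicts choline pool size universally". Section 6.4 pools 50 completers from each of three groups and aims to "identify a formula for composite score that can predict choline pool size for all three groups". For Aim 1, neither section names weight, lean mass, body composition, sex or subject as a term, and neither rescales the pool.
- **Interpretation.** The end of section 1.1 treats prediction of total pool size as prediction of nutritional status. The Synopsis (Efficacy Evaluations) sets the bar at more than 90% accuracy in predicting pool size and does not define accuracy.
- **Body size elsewhere.** Sections 1.2 and 7 define choline intake per 70 kg body weight. Section 4.2 collects body composition at the first and last visit of each arm; at Visit 7, for example, "A heart rhythm strip and body composition measure will be obtained".
- **Fallback.** If the universal score performs poorly, section 6.4 analyses each group separately. Section 6.3 words this as each diet period separately.

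**The concern.** A whole-body amount can be larger because the person is better supplied with choline or because the person is bigger. The score is meant to measure the first. If the pool grows with body size, a heavy depleted subject can have a larger b than a light replete subject, and the model is trained to rank them that way.

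The error can go in either direction:

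- Markers that reflect status but not size miss the size-related variance, so a good panel looks weak against the accuracy bar.
- The supervised fit and the VIP selection can favour markers that follow sex or muscle mass. CK is in the panel, and the upper limits in Appendix Figure 6 differ by sex (204 v 173 U/L). SubAim 1b adds untargeted features. Such a score would look good for the wrong reason.

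The score is then the response in SubAim 1c, so any size component is carried into the genotype comparisons.

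**Working it through.** **The plan's own figure.** 50 × 3 = 150 completers; 150/(1 − 1/6) = 180 recruited. Both agree with sections 3.3 and 6.4. Aim 1 has no power formula to reproduce, because section 6.4 says its sample size rests on prediction accuracy.

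**Step 1. Is b absolute?** The isotope abundances are ratios, so b has the unit of a. The documents describe the label both as a 250 mg bolus on day 12 (Synopsis, sections 3.1 and 7) and as 22% of dietary choline over the last 5 days (sections 1.2 and 5.1). Those passages must be reconciled, but b is an amount under either.

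**Step 2. Ceiling on R2.** Suppose pool = weight^e × size-adjusted pool, with the two factors independent, and use CVs as SDs on the log scale. A score that captures size-adjusted pool perfectly and carries no size information has

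R2 max = CVs² / (CVs² + (e × CVw)²),

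where CVs is the CV of size-adjusted pool and CVw that of body weight. The documents give none of CVs, CVw or e; all are assumed.

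| CVw | e | CVs 10% | 15% | 20% | 30% | CVs needed for R2 = 0.90 |
|---|---|---|---|---|---|---|
| 12% | 0.5 | 0.74 | 0.86 | 0.92 | 0.96 | 18% |
| 15% | 0.5 | 0.64 | 0.80 | 0.88 | 0.94 | 22.5% |
| 20% | 0.5 | 0.50 | 0.69 | 0.80 | 0.90 | 30% |
| 12% | 1 | 0.41 | 0.61 | 0.74 | 0.86 | 36% |
| 15% | 1 | 0.31 | 0.50 | 0.64 | 0.80 | 45% |
| 20% | 1 | 0.20 | 0.36 | 0.50 | 0.69 | 60% |

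Example: CVw 20%, e = 1, CVs 10% gives 0.01/(0.01 + 0.04) = 0.20. The last column is 3 × e × CVw, because R2 = 0.90 requires CVs² = 9(e × CVw)².

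**Step 3. Split of log-pool variance into body size, diet and other.**

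- Assumed heights: 176 cm (SD 7) in men, 163 cm (SD 6.5) in women.
- Assumed BMI: uniform on 18.5 to 32, or normal 25.5 (SD 2.5) clipped to that range. The upper limit is the entry criterion in section 3.4. Weight CV is then about 15 to 19%.
- Low-diet pool ratio: 0.67 to 0.89. These are the depletion/baseline ratios for plasma choline and total phosphatidylcholine in the fatty-liver group of Appendix Figure 3 (earlier 10% diet), borrowed as stand-ins for the pool. The middle diet is interpolated linearly.
- Other between-subject CV: 5 to 20%.

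Results:

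- e = 1: body size is 24 to 88% of log-pool variance (36 to 75% at 10% other CV); diet is 3 to 53%.
- e = 0.5: body size is 7 to 65%.
- Analysing each group separately (e = 1, 10% other CV): the extremes of 75% and 36% become 72% and 30%.
- Pool per kg instead (e = 1, 10% other CV, uniform BMI): the diet share rises from 5 to 19% at ratio 0.89, from 16 to 46% at 0.80, and from 37 to 73% at 0.67.

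**Step 4. Ranking example under proportionality.** A 95 kg subject at ratio 0.67 has index 95 × 0.67 = 63.7. A 55 kg replete subject has 55. Absolute pool ranks the depleted subject higher.

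**The case against.** - **Each subject is their own control (sections 3.1 and 6.3).** This protects within-subject contrasts. So does the argument in section 5.1 that constant errors leave changes in pool size unaffected. The Aim 1 model is fitted to levels, so neither applies.
- **The by-group fallback.** It is partial mitigation. It starts only if the universal score performs poorly, and a score that does well by tracking size would not trigger it. It removes between-group size differences only. Read literally as separate diet periods (section 6.3), it would remove diet variation and raise the body-size share.
- **The pool may not follow body weight.** This stands. Section 5.1 says b is the pool that dietary choline reaches within 5 days, likely smaller than the total body pool, and stresses liver storage. Nothing in the documents says that this scales linearly with weight.
- **Adjustment can remove real signal.** This also stands. Sections 1.1 and 5.1 link sex, menopausal status and oestrogen-driven synthesis to choline requirement and depletion, so group terms in the main model could absorb true status differences. Weight could do the same if intake is flat: 550 mg is 10.0 mg/kg at 55 kg and 5.8 mg/kg at 95 kg. The Synopsis gives intake both per 70 kg and as flat mg per day.

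**Conclusion.** The gap is established from the text: the outcome is an absolute amount, pooled over three groups, read as status, with no body-size term although body composition is measured. Its size is not established. Across the assumed ranges the R2 ceiling is 0.20 to 0.74, 0.36 to 0.86, 0.50 to 0.92 and 0.69 to 0.96 for size-adjusted CVs of 10, 15, 20 and 30%.

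A reader might infer that most of the outcome is body mass, or that a perfect status panel must miss the accuracy bar. The documents support neither. The first needs a weight SD and a pool-to-weight relation that they do not give, and the body-size share falls to 7% in the mildest case examined. The second reads the 90% accuracy criterion as R2, which the plan never says; even on that reading some combinations in the table pass.

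This should be changed before the model is fitted. It does not affect sample size or conduct.

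**What to change.** In section 6.3, Aim 1:

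1. Model log pool size with log body weight as a covariate, or lean mass if the body composition measure provides it. Re-estimate its coefficient inside each bootstrap resample, so that the scaling exponent is estimated and not assumed.
2. Report the score's R2 over and above body size.
3. Report how well the score predicts within-subject change in log pool size between diets. A stable body-size factor cancels from that contrast.
4. Give pool per kg, and adjustment for sex/menopausal group, as sensitivity analyses.
5. State the unit of the pool and define the accuracy criterion.
6. Reconcile the per-70-kg and flat statements of intake, because the meaning of the weight coefficient depends on which applies.

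Cost: SAP wording and slightly more analysis, using body-size data from visits already planned. The downside is that the body-size coefficient may absorb some true depletion if intake is flat; items 3 and 4 help to show whether it does.
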